**ClinicalTrials.gov Identifier: NCT04638127**

**NIH NINR: 1K23NR019081**

**Document Date: 2020-10-22**

## Study Protocol and Statistical Analysis Plan

# Study Protocol

## Study Description

The purpose of this study is to refine and pilot test a mobile health (mHealth), video-based family management program for parents of preterm infants hospitalized in the Neonatal Intensive Care Unit (NICU). By moving beyond the basic infant care tasks taught by parenting programs and instead comprehensively training parents to use evidence-based family management skills, we hypothesize that our intervention, called PREEMIE PROGRESS, will better equip parents to meet the chronic, complex healthcare needs of their preterm infant.

## Detailed Description:

Increasing numbers of very preterm infants are surviving and have chronic, complex healthcare needs due to prematurity. These infants experience increased healthcare utilization, long durations of stay in the Neonatal Intensive Care Unit (NICU), and are at high risk of developing prematurity-related complications. As a result, their care is complex, and families need structured training to effectively understand, monitor, and manage their infant's care. PREEMIE PROGRESS is an innovative, video-based intervention that applies evidence-based family management theories to better equip parents to meet the chronic, complex healthcare needs of their preterm infant. This research aims to 1) refine a novel family management program, called PREEMIE PROGRESS, through iterative usability and acceptability testing and 2) test feasibility and acceptability of the refined intervention and study procedures in a pilot randomized controlled trial. This project will use implementation science tools and approaches to refine the intervention and study procedures to ensure that PREEMIE PROGRESS addresses key program elements that will be important for future adoption and implementation in NICU settings. We anticipate that the intervention will decrease parent anxiety and depression, increase infant weight gain and receipt of mother's milk, and reduce neonatal healthcare utilization. The long-term goal of this project is to develop, test, and translate into NICU practice an efficacious family management intervention for parents of preterm infants. [name] will significantly advance nursing science through this project by obtaining preliminary feasibility and acceptability data for a scalable and sustainable intervention to facilitate family management and improve parent-infant health outcomes.

## Study Design

Study Type: Interventional (Clinical Trial)

Primary Purpose: Supportive Care

Intervention Model: Parallel Assignment

Actual Enrollment: 44 Participants

Number of Arms: 2

Masking: Triple (Participant, Care Provider, Outcomes Assessor)

Allocation: Randomized

Enrollment [Actual]: 64 mothers of very preterm infants

## Arms and Interventions:

**PREEMIE PROGRESS arm:** PREEMIE PROGRESS is an innovative, video-based intervention that applies evidence-based family management theories to better equip parents to meet the chronic, complex healthcare needs of their preterm infant. PREEMIE PROGRESS is a video-based training program for parents of preterm infants hospitalized in the neonatal intensive care unit (NICU).

**Attention Control arm:** To maintain their attention, control parents will view "Welcome Videos" that explain hand hygiene, visitor IDs, parking, etc. on their mobile devices.

## Randomization

Using STATA software, the Statistician will generate a random allocation sequence stratified by GA at birth (GA <28 weeks and >28 weeks) to balance representation of the youngest and sickest infants. We will use permuted block randomization for each stratum, with block sizes of 2, 4, and 6 and a 1:1 treatment allocation. The Statistician will upload the sequence into REDCap, have no contact with subjects, and will be independent of all assessment procedures. REDCap's secure randomization feature prevents the study team from viewing the treatment allocation sequence, ensuring allocation concealment. Research assistants will enroll and collect baseline data before randomization. The Principal Investigator (PI) / Clinical Research Coordinator (CRC) will randomize each family after baseline survey completion to minimize dropout effects on randomization.

## Eligibility Criteria

### Inclusion Criteria:

- English-speaking parents
- Parents preterm infants born 25 0/7-31 6/7 weeks gestational age (GA)
- Parents who had a singleton or twin birth
- Parents 18 years of age or older

### Exclusion Criteria:

- Mothers too ill (serious maternal complications, medications that impact alertness/ orientation) to provide informed consent
- Infants with imminent or probable death based on the healthcare team's judgement

## Outcome Measures

Measure Title	Maternal Self-Rating of Depression
Measure Description	Patient-Reported Outcomes Measurement Information System (PROMIS) 8a Higher scores indicate higher levels of depression: T-score: standardized score mean of 50 and standard deviation (SD) of 10
Time Frame	Assessed at Baseline 14 days post-baseline (T2), 28 days post-baseline (T3), and 30 days after infant discharge from the NICU (T4). Change from Baseline to 30 days after infant discharge from the NICU (T4) Reported.
Measure Title	Maternal Self-Rating of Anxiety
Measure Description	Patient-Reported Outcomes Measurement Information System (PROMIS) 8a Higher scores indicate higher levels of anxiety: T-score: standardized score mean of 50 and standard deviation (SD) of 10
Time Frame	Assessed at Baseline, 14 days post-baseline (T2), 28 days post-baseline (T3), and 30 days after infant discharge from the NICU (T4). Change from Baseline to 30 days after infant discharge from the NICU (T4) Reported.
Measure Title	Receipt of Mother's Human Milk
Measure Description	(exclusive, partial, none).
Time Frame	Assessed at Baseline, 14 days post-baseline (T2), 28 days post-baseline (T3). Reported here is 28 days post-baseline (T3).
Measure Title	Z Score of Weight Gain at 36 Weeks Corrected Gestational Age
Measure Description	Z-score method; Z score $\Delta$ weight (g), Birthweight (g) - infant weight (g) at 36 weeks corrected gestational age
Time Frame	Calculated for the date that infant is 36 weeks corrected gestational age
Measure Title	NICU Length of Stay
Measure Description	Days of NICU hospitalization (calculated from days between date of birth to date of discharge from NICU)
Time Frame	Date of NICU discharge will be assessed until study completion, with maximum of 1 year
Measure Title	Infant Hospital Readmissions and Emergency Department Visits Within 30 Days of Infant Discharge.
Measure Description	Coded as Yes/No and extracted from the infant's electronic health record. Mothers were also asked "Did your infant have any re-hospitalizations or emergency department visits within 30 days of discharge?", to ensure all rehospitalizations and ED visits were captured.
Time Frame	Readmissions/ER visits counted within 30 days of discharge will be assessed date of NICU discharge will be assessed until study completion, with maximum of 1 year

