### Analysis

REDCAP data will be exported to Stata 15 software, where we will analyze sources of missing data and calculate descriptive/summary statistics. We will graph trends for all variables over infant Day of Life (DOL) and CGA, comparing boxplots between arms and over time. We will compute means and 95% CIs for changes from baseline (T1 to T2-4) for each outcome by arm. At each follow-up (T2-4), we will compute mean differences and 95% CI between arms to evaluate trends in outcomes. Mothers with multiple births will have one infant randomly selected for analysis. We will not test for statistically significant differences between groups in outcome measures or estimate effect sizes in this pilot study, because the primary purpose is to determine feasibility of our procedures to inform the planning and design of a larger trial.

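### The weight-gain z-score is defined by a birthweight-first expression in grams: read as subtraction it scores better growth lower, and no growth reference is named

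*Combined protocol and SAP*

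**What the plan says.** The Outcome Measures section titles the outcome "Z Score of Weight Gain at 36 Weeks Corrected Gestational Age". Its description is "Z-score method; Z score $\Delta$ weight (g), Birthweight (g) - infant weight (g) at 36 weeks corrected gestational age", and its time frame is "Calculated for the date that infant is 36 weeks corrected gestational age". This is the only place where the documents say how the outcome is built. No growth chart, reference population, reference mean or reference SD appears anywhere, and the row has no sentence on what a higher value means.

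Three other places bear on the intended direction:

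- The Detailed Description expects the intervention to "increase infant weight gain and receipt of mother's milk".
- The PROMIS rows in the same table give a metric and a direction (for depression, "Higher scores indicate higher levels of depression") and describe change forwards in time: "Change from Baseline to 30 days after infant discharge from the NICU (T4) Reported".
- The Analysis section of the SAP also describes change forwards: "We will compute means and 95% CIs for changes from baseline (T1 to T2-4) for each outcome by arm".

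**The concern.** The title and the stated aim point one way, and the only expression given points the other if its separator is a minus sign. Birthweight minus a later weight is negative for any infant who has gained weight, and it becomes more negative the better the infant grows.

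The expression is also in grams under a title that promises a z-score. The grams may simply be the raw inputs to a change in z-score, but the row does not say so. Without a named reference, two analysts given the same weights could produce different values.

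At stake is the sign of an infant growth outcome. If the written order were applied in z units, growth that favoured the intervention would be reported as favouring control. The pilot is meant to inform a larger trial, so the definition could be reused there.

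**Working it through.** The documents give no figure for this outcome, so there is nothing to reproduce. The check is on the expression itself, with assumed weights and reference values used only to show direction.

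**1. Minus sign or dash?** The symbol follows a Δ and stands, with spaces, between two quantities that each carry a gram unit. Where the documents mean a span they use the word to, as in "Change from Baseline to 30 days after infant discharge from the NICU (T4) Reported", or an unspaced hyphen, as in "born 25 0/7-31 6/7 weeks gestational age (GA" and in T2-4 in the Analysis section. That makes subtraction the more natural reading, but it does not exclude a dash.

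**2. Direction if it is subtraction.** Assume three infants with birthweight 1000 g and 36-week weights of 2000, 2300 and 2600 g, so the third grows best.

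- *Grams:* 1000 − 2000 = −1000; 1000 − 2300 = −1300; 1000 − 2600 = −1600. The best grower scores lowest.
- *Within-sample z of that difference* (mean −1300, SD 300): +1, 0, −1. The best grower again scores lowest.
- *z at birth minus z at 36 weeks*, with an assumed birth reference of mean 1100 g, SD 200 g and an assumed 36-week reference of mean 2600 g, SD 400 g: z at birth = (1000 − 1100)/200 = −0.50; z at 36 weeks = −1.50, −0.75 and 0.00; differences = +1.00, +0.25 and −0.50. The best grower scores lowest once more.

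The ordering is inverted on all three scales, for any positive reference SD. Putting the later weight first gives +1000, +1300 and +1600 g, or −1.00, −0.25 and +0.50 z, and restores it.

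**3. Would a reversal show?** In grams, yes. From the eligibility range, the time from birth to 36 weeks 0 days runs from 252 − 223 = 29 days (born at 31 weeks 6 days) to 252 − 175 = 77 days (born at 25 weeks 0 days), so practically every value would be negative. In z units the sign alone need not give it away: in step 2 both orders give a mixture of positive and negative values.

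**4. Dependence on the reference.** Take the 2300 g infant, keep the assumed birth reference, and vary only the 36-week reference. Conventional change = z at 36 weeks − (−0.50).

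| Assumed 36-week mean, SD (g) | z at 36 weeks | Change |
|---|---|---|
| 2500, 350 | −0.57 | −0.07 |
| 2600, 400 | −0.75 | −0.25 |
| 2800, 450 | −1.11 | −0.61 |

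One pair of weights gives a change anywhere from −0.07 to −0.61, depending only on the reference chosen.

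**5. Effect on an arm comparison, hypothetical.** Let D = (z36 − zB) in the intervention arm minus (z36 − zB) in the control arm. The written order gives −D, which is 2D away from D. For example, with assumed z of 0 at birth in both arms and −0.6 (intervention) versus −0.8 (control) at 36 weeks, D = −0.6 − (−0.8) = +0.2. The written order gives 0.6 − 0.8 = −0.2, from arm values of +0.6 and +0.8 that look like gains. This is an identity with assumed inputs, not an estimate for this trial.

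**The case against.** The strongest reply is that the Δ already denotes the change and the words after the comma only name its two endpoints, birthweight to 36-week weight. On that reading nothing is reversed. This cannot be ruled out, and it is why the sign objection is conditional. It does not rescue the row as a definition, because the operation, the scale and the reference would still be unstated.

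A second reply is that the direction is not really in doubt: the title speaks of weight gain and the Detailed Description expects an increase. That stands. Both imply that higher means more gain, and the milk, length-of-stay and readmission rows have no direction sentence either. The missing sentence would be a small matter alone. It matters here because the only expression given appears to contradict what the title implies.

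A third reply is that the evidence of intent suggests a slip of wording rather than a reversed analysis. That is also fair. A reader might infer that the trial's growth results carry the wrong sign. The documents do not support this: they contain no results for the outcome and do not show whether the order, or the gram units, were used as written.

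Finally, this is a feasibility pilot. The Analysis section rules out significance tests and effect-size estimates, and it does not clearly assign this outcome a between-arm summary, since its planned differences are at T2-4 and this outcome is one value at 36 weeks. That limits the consequence; it does not make the expression right.

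**Conclusion.** The concern holds as a defect in the outcome definition. On the more natural reading, the stated rule scores better growth lower and conflicts with its own title and with the anticipated benefit. On either reading, grams are given where a z-score is named, and the z-score cannot be reproduced because no reference is identified.

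The conclusion about sign rests on the separator being a minus sign. Any reversal in reported values rests further on the written order having been followed, which the documents do not show. No size can be given for this trial: D becoming −D is the form an error would take, and the values of D and z used above are assumptions. The reach is one of six listed outcomes. It is worth fixing because a literal reader would compute the wrong sign, the values in z units need not reveal it, and the correction is very cheap.

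**What to change.** Replace the description with: change in weight z-score, defined as z(weight at 36 weeks CGA) minus z(birthweight), both from one named preterm growth reference, with a higher value meaning better growth. Delete the birthweight-first gram expression.

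Then check how any existing values were computed. Re-sign those that used the written order, recompute those that used grams in place of z-scores, and leave the rest alone.

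The cost is one line of wording and the name of a reference. Both weights are already named in the outcome, and gestational age at birth is already used for eligibility and stratification. New data would be needed only if a sex-specific reference were chosen and infant sex had not been recorded; the documents do not mention it.

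### The birth-to-36-week weight endpoint counts growth before randomisation, which costs precision but does not bias the comparison; adjusting for that growth recovers the loss

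*Combined protocol and SAP*

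**What the plan says.** Outcome Measures lists a z score of weight gain with the component "Birthweight (g) - infant weight (g) at 36 weeks corrected gestational age" and the time frame "Calculated for the date that infant is 36 weeks corrected gestational age". I read this as the change from birth to 36 weeks. The order of subtraction gives a gain a negative sign, but that is a separate matter.

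Inclusion Criteria admit "Parents who had a singleton or twin birth", with gestational age (GA) at birth from 25 0/7 to 31 6/7 weeks. The birth has therefore already happened when a family qualifies. Randomization then states: "Research assistants will enroll and collect baseline data before randomization". It adds that the study team "will randomize each family after baseline survey completion to minimize dropout effects on randomization".

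No section gives a latest day of life or corrected GA for enrolment, baseline or randomisation. The inclusion criteria cover language, GA at birth, plurality and parental age. The exclusion criteria cover mothers too ill to consent and "Infants with imminent or probable death based on the healthcare team's judgement". The only implied bound is in Study Description, where the infants are described as hospitalised in the NICU.

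The Analysis section plans between-arm mean differences with 95% CIs. It mentions no adjustment for age, weight or growth at randomisation.

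**The concern.** A between-arm comparison can only show what happens after allocation. Here the outcome clock starts at birth, so each infant's value is the sum of two parts: growth up to randomisation, which the videos cannot influence, and growth afterwards, which they might. The first part adds variance and no information about the intervention.

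What is at stake is the width of the interval for an outcome that the Detailed Description names among the anticipated benefits. The Power section says there were no reliable prior estimates of standard errors or mean differences, and the Analysis section says the pilot is to inform a larger trial. Precision for this endpoint, and how much of its window remains once a family is randomised, are therefore useful products of the pilot.

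**Working it through.** The plan states no figure on this point, so there is none to reproduce. The check is calendar arithmetic followed by a simple variance model.

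**Inputs from the document.** GA at birth is 25 0/7 to 31 6/7 weeks (Inclusion Criteria). The endpoint closes at 36 0/7 weeks (Outcome Measures). The aim was at least 30 mothers per arm (Power).

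**Assumed.** Randomisation takes place 3, 7 or 14 days after birth.

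**Step 1: window length.** Window = 36 × 7 − GA at birth in days.
- Born 25 0/7: 252 − 175 = 77 days.
- Born 31 6/7: 252 − 223 = 29 days.

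**Step 2: share of the window past at randomisation.** Share = day of randomisation / window.

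| GA at birth | Window (days) | Day 3 | Day 7 | Day 14 |
|---|---|---|---|---|
| 25 0/7 | 77 | 3.9% | 9.1% | 18.2% |
| 28 0/7 | 56 | 5.4% | 12.5% | 25.0% |
| 30 0/7 | 42 | 7.1% | 16.7% | 33.3% |
| 31 6/7 | 29 | 10.3% | 24.1% | 48.3% |

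The window is fully past from day 29 for birth at 31 6/7 and from day 77 for birth at 25 0/7. For an infant born at 31 6/7, the 28-day assessment (T3) falls after the weight endpoint if baseline is later than day 1.

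**Step 3: from days to variance.** Assume that z-score change accumulates in independent daily steps of equal variance, and that GA is spread evenly over the eligible range. The mean window is then (77 + 29)/2 = 53 days, and the pre-randomisation share of the variance is:
- day 3: 3/53 = 0.06
- day 7: 7/53 = 0.13
- day 14: 14/53 = 0.26

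**Step 4: effect on the interval.** Narrowing = 1 − √(1 − share).
- day 3: 1 − √(50/53) = 2.9%
- day 7: 1 − √(46/53) = 6.8%
- day 14: 1 − √(39/53) = 14.2%

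**Step 5: absolute scale.** With 30 per arm, the 95% half-width for a mean difference is about 2.00 × √(2/30) = 0.52 SD. The narrowing would bring it to about 0.50, 0.48 or 0.44 SD. Estimating one extra coefficient gives back about 1% of the width at this sample size.

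**Sensitivity of step 3.** The gain depends on how growth before randomisation relates to the total change. If early and later growth are positively correlated, adjustment removes more variance than shown. If they are negatively correlated, it can remove less, down to nothing when early growth is unrelated to the total. Differences in mean z-score change across GA at birth would also lower the pre-randomisation share.

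**The case against.** The strongest reply is that this changes no conclusion the plan intends to draw. The pilot is about feasibility, is not powered for outcomes, and plans no significance tests or effect-size estimates. A half-width of 0.48 SD in place of 0.52 SD leaves the result just as inconclusive. The size also rests on an assumed age at randomisation and an untested growth model. This stands, and it is why the priority is not higher.

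Three stronger readings are tempting, and the document does not support them.
- A reader might infer that the endpoint is biased. Growth before allocation is balanced between arms in expectation, so what remains is noise and chance imbalance.
- A reader might infer that some infants' outcomes were complete before randomisation, pulling the difference toward zero. The text leaves this open, and the one-year maximum for recording NICU discharge allows for stays beyond 36 weeks. But it requires a family newly randomised with an infant still in the NICU at that age, and nothing shows that any were.
- A reader might infer that the SD passed to the main trial would be wrong. If that trial keeps this endpoint and analyses it unadjusted, the unadjusted SD is the right one. An SD from 60 infants is in any case uncertain by about −15% to +22%.

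It can also be said that the Analysis section already plans changes from T1 for each outcome. Taken literally, that would anchor weight at baseline, but it conflicts with the definition in Outcome Measures and does not say how a birth-anchored measure is to be handled.

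**Conclusion.** The point holds as one of precision. The endpoint includes growth before randomisation for every infant, and the plan makes no allowance for it. Under the stated assumptions, adjustment would narrow the interval by about 3% for randomisation at day 3, 7% at day 7 and 14% at day 14. If families were randomised within the first few days, the gain is close to negligible. For later-born infants randomised in the second week, a quarter to a half of the window is already past.

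No bias is shown, and no infant is shown to have been randomised at or after 36 0/7 weeks. The absence of a stated limit is a gap to be closed by reporting. Low to moderate priority.

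**What to change.** Keep the birth-to-36-week endpoint and add the following to the Analysis section.

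1. Estimate the between-arm mean difference and 95% CI with adjustment for the z-score change from birth to the last weight before randomisation, and show it beside the unadjusted result. The covariate is fixed before allocation, so it introduces no bias.
2. Report day of life and corrected GA at randomisation by arm. This shows how much of the window was left and replaces the assumed ages above.
3. If any infant was randomised at or after 36 0/7 weeks, leave that infant out of this one analysis, give the number by arm, and state that the analysed population is narrowed. The rule uses only information available before allocation, so it introduces no selection bias, but it does change the population to which the estimate refers. It does not remove infants randomised shortly before 36 0/7 weeks; the report of corrected GA will show how many there are.

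The cost is one weight per infant, one model term in a plan of otherwise simple means, and possibly a few infants not counted for this endpoint. The Analysis section says "We will graph trends for all variables over infant Day of Life (DOL) and CGA", which suggests that serial weights may exist, but Outcome Measures names only birthweight and the 36-week weight. The document reports actual enrolment, so the extra weight may have to be abstracted from the chart retrospectively. In that case, label the adjusted analysis with the date it was added.

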### Power

We aimed to enroll at least 60 mothers (30 mothers per arm), with planned over recruitment to account for up to 20% loss to follow-up (i.e., 72 infants) during the pilot trial. Because we did not have reliable estimates for the confidence intervals, standard errors, or mean differences for our outcomes a priori, our sample size was based on Whitehead's recommendations to have at least 20 persons per treatment arm in a pilot trial when expecting a small standardized difference ( $\delta=0.2$ ) to achieve at least 80% in the main trial. Because our emphasis was on feasibility, this pilot trial was not powered to detect statistically significant changes in outcome and mediating variables between arms.

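### No between-arm analysis of NICU length of stay uses gestational age at birth, a known pre-randomisation stratifier, so the interval will be wider than data already held allow

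*Combined protocol and SAP*

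**What the plan says.** Under Outcome Measures, NICU length of stay is "Days of NICU hospitalization (calculated from days between date of birth to date of discharge from NICU". The clock starts at birth and is not indexed to maturity. The Inclusion Criteria admit "Parents preterm infants born 25 0/7-31 6/7 weeks gestational age (GA").

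GA at birth is already in hand when the family is randomised. The Randomization section says allocation is "stratified by GA at birth (GA <28 weeks and >28 weeks) to balance representation of the youngest and sickest infants", so the plan itself treats GA as prognostic.

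The Analysis section plans between-arm mean differences with 95% confidence intervals at T2 to T4. It names no covariate and no stratum term. Length of stay is not a T2 to T4 measure, and no other between-arm method is given for it. Corrected GA does appear in that section, but as a plotting axis: "We will graph trends for all variables over infant Day of Life (DOL) and CGA".

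**The concern.** If readiness for discharge depends largely on maturity, an infant born at 25 weeks stays several weeks longer than one born near 32 weeks, whichever arm the mother is in. Days from birth then contain a large component that was fixed before randomisation. An unadjusted comparison leaves that component in the error term. It also ignores the strata used to allocate, so its interval is wider than the design justifies.

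The stake is precision. Reduced healthcare utilisation is one of the effects the Detailed Description anticipates, and length of stay is one of two outcomes that bear on it. The Power section says that reliable standard errors and mean differences were not available beforehand, so the pilot's estimates of variability are among its main products for planning.

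**Working it through.** The plan gives no SD, slope or interval width for length of stay, so there is no figure of its own to reproduce on this point. The values marked as assumed are not in the documents.

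**Inputs**
- GA window (Inclusion Criteria): 25 × 7 = day 175 to 31 × 7 + 6 = day 223, which is 49 possible days.
- Strata (Randomization): cut at 28 weeks, so bands of about 21 and 28 days.
- Size (Power): "We aimed to enroll at least 60 mothers (30 mothers per arm"), so n = 30.
- Assumed: GA uniform within each stratum; 25% or 40% of infants below 28 weeks; slope b of stay on GA from −0.8 to −1.3 days per day; residual SD s from 10 to 21 days. Middle case: b = −1, s = 14.

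**Variance of GA**
- Within strata: 21²/12 = 36.75 and 28²/12 = 65.33. Weighted, Vw = 58.2 (25% below 28 weeks) or 53.9 (40%).
- Between strata: midpoints 24.5 days apart, so p(1−p) × 24.5² = 112.5 or 144.1.
- Total V = 170.7 or 198.0.

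**Middle case.** Half-width = 2.00 × SD × √(2/30) = 0.516 × SD.

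| Analysis | Variance | SD (days) | Half-width (days) |
|---|---|---|---|
| Unadjusted | s² + b²V = 366.7 or 394.0 | 19.1 or 19.8 | 9.9 or 10.3 |
| Using the 28-week stratum | s² + b²Vw = 254.2 or 249.9 | 15.9 or 15.8 | 8.2 |
| Adjusting for GA in days | s² = 196 | 14.0 | 7.2 |

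The variance reduction is 170.7/366.7 = 47% or 198.0/394.0 = 50% against the unadjusted analysis. Against an analysis that uses the stratum it is 58.2/254.2 = 23% or 53.9/249.9 = 22%.

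**Full assumed range.** The smallest gain is at b = −0.8, s = 21 and the largest at b = −1.3, s = 10. Against the unadjusted analysis the reduction is 20% to 77%; beyond the stratum it is 7% to 50%.

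**True standard error.** Stratified allocation already balances most of the between-stratum part, so the unadjusted difference really varies roughly as s² + b²Vw, while its interval is computed from s² + b²V. In the middle case the true standard error falls by 1 − 14/15.9 = 12% (11% at 40% below 28 weeks), whereas the interval narrows by 27% to 29%. A simulation of 20,000 trials (30 per arm, slope −1.2, residual SD 20, GA-stratified allocation) shows the same mismatch: the unadjusted 95% interval covered 98% of the time.

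**Corrected GA at discharge as an alternative.** It equals GA at birth plus days of stay. GA precedes randomisation, so the expected between-arm difference is the same. Its variance is s² + (1+b)²V, which is below s² + b²V only if b < −0.5. With GA uniform over the whole window (SD 14.1 days) and residual SD 10 to 30, the interval is 10% to 42% narrower at b = −1, unchanged at b = −0.5, and 2% to 14% wider at b = −0.4.

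**Sample size actually reached.** The Study Design section gives two enrolment figures, one being "Actual Enrollment: 44 Participants". At 22 per arm, with b = −1, s = 15 and uniform GA, the half-widths are 12.5 days unadjusted and 9.1 adjusted. At 30 per arm they are 10.7 and 7.8. The relative gain is 27% either way.

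**Planning.** Required size scales with variance. If the larger trial adjusts for GA in days, carrying forward the raw SD would overstate its size for this outcome by 366.7/196 = 1.9 to 394.0/196 = 2.0 times. Carrying forward the within-stratum SD would overstate it by about 1.3 times.

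**The case against.** The strongest reply is that the design has already done most of the work. With GA uniform over the window, stratifying at 28 weeks removes about 73% of the GA variance from the true between-arm error. In the middle case about 2 of the roughly 3 days gained in half-width come simply from using the stratum in the analysis; GA in days adds about one more. This stands, and it is why the 47% to 50% figure must not be read as the gain from GA in days alone.

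A reader might infer that chance GA imbalance could pass for a utilisation effect. The documents do not support that as a serious risk. Allocation within strata uses "block sizes of 2, 4, and 6 and a 1:1 treatment allocation", so mainly within-stratum imbalance remains, and the unadjusted interval errs towards being too wide.

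A reader might also infer that days from birth is the wrong scale and that corrected GA at discharge should replace it as an equivalent with a narrower interval. It is not equivalent: it fixes the slope at −1, whereas regression estimates it. It helps only if each extra day of GA shortens stay by more than half a day, and the documents give no slope. Days of stay is also a direct count of utilisation.

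Finally, this is a feasibility pilot that does no testing and is not powered for outcomes, and the T2 to T4 wording leaves it unclear which comparison of stay is intended. Both points stand. They limit the consequence, but they do not justify leaving out a baseline value already collected.

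**Conclusion.** The point holds as a matter of precision. No analysis of length of stay in the plan uses GA at birth, although GA is held before randomisation and stratified on. In the middle case, adjusting for GA in days brings the half-width from about 9.9 to 10.3 days down to 7.2, of which the step beyond the stratum is 8.2 to 7.2. The gain in true standard error is smaller, about 11% to 12% there.

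All these sizes rest on assumed slopes, residual SDs and GA distributions, with a linear relation and constant residual spread. How much of the spread in stay is due to GA cannot be fixed from the documents: with uniform GA and residual SD 10 to 30 days, it is 18% to 67% at slope −1 and 10% to 49% at slope −0.7. In large samples, adjustment is at least as precise as either raw days or corrected GA at discharge, whatever the slope. A reader might conclude that the current plan would mislead the pilot; it would not, because no pilot conclusion turns on this interval.

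**What to change.** Keep days of stay as the outcome and report raw days by arm. Add to the Analysis section:

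> The between-arm difference in NICU length of stay will be estimated by linear regression on arm, adjusting for GA at birth in days, and reported in days with its 95% CI.

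This also supplies the method for length of stay that the T2 to T4 wording leaves out. Report the residual SD beside the raw SD for use in planning. Corrected GA at discharge may be shown as a supplementary description, not as a substitute.

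The cost is one sentence and one degree of freedom, with no new data and no change to the stated outcome. Because the Study Design section already reports actual enrolment, the addition should be dated and labelled supplementary, with a note on whether outcome data had been seen.
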